3.3 SELECTION OF TRIAL POPULATION

It is planned that 18 (Part 1) and 14 (Part 2) healthy male or female subjects will enter the study. They will be recruited from the volunteer's pool of the trial site.

A log of all subjects enrolled into the trial (i.e. who have signed informed consent) will be maintained in the ISF irrespective of whether they have been treated with investigational drug or not.

3.3.1 Main diagnosis for trial entry

The study will be performed in healthy subjects.

3.3.2 Inclusion criteria

Subjects will only be included in the trial if they meet the following criteria:

1. Healthy male or female subjects according to the assessment of the investigator, as based on a complete medical history including a physical examination, vital signs (BP, PR), 12-lead ECG, and clinical laboratory tests
2. Age of 18 to 50 years (inclusive)
3. BMI of 18.5 to 29.9 kg/m² (inclusive)
4. Signed and dated written informed consent prior to admission to the study, in accordance with GCP and local legislation
5. Male subjects, or female subjects who meet any of the following criteria from the first administration of trial medication until 30 days after trial completion:
 - Use of adequate contraception that does not contain hormones, i.e. non-hormonal intrauterine device *plus* condom
 - Sexually abstinent
 - A vasectomised sexual partner (vasectomy at least 1 year prior to enrolment)
 - Surgically sterilised (including hysterectomy)
 - Postmenopausal, defined as at least 1 year of spontaneous amenorrhea (in questionable cases a blood sample with levels of FSH above 40 U/L and estradiol below 30 ng/L is confirmatory)

3.3.3 Exclusion criteria

Subjects will not be allowed to participate, if any of the following general criteria apply:

1. Any finding in the medical examination (including BP, PR or ECG) deviating from normal and assessed as clinically relevant by the investigator
2. Repeated measurement of systolic blood pressure outside the range of 90 to 140 mmHg, diastolic blood pressure outside the range of 50 to 90 mmHg, or pulse rate outside the range of 50 to 90 bpm

3. Any laboratory value outside the reference range that the investigator considers to be of clinical relevance
4. Any evidence of a concomitant disease assessed as clinically relevant by the investigator
5. Gastrointestinal, hepatic, renal, respiratory, cardiovascular, metabolic, immunological or hormonal disorders
6. Cholecystectomy or other surgery of the gastrointestinal tract that could interfere with the pharmacokinetics of the trial medication (except appendectomy or simple hernia repair)
7. Diseases of the central nervous system (including but not limited to any kind of seizures or stroke), and other relevant neurological or psychiatric disorders
8. History of relevant orthostatic hypotension, fainting spells, or blackouts
9. Chronic or relevant acute infections
10. History of relevant allergy or hypersensitivity (including allergy to the trial medication or its excipients)
11. Use of drugs within 30 days of planned administration of trial medication that might reasonably influence the results of the trial (including drugs that cause QT/QTc interval prolongation)
12. Intake of an investigational drug in another clinical trial within 60 days of planned administration of investigational drug in the current trial, or concurrent participation in another clinical trial in which investigational drug is administered
13. Smoker (more than 10 cigarettes or 3 cigars or 3 pipes per day)
14. Inability to refrain from smoking on specified trial days
15. Alcohol abuse (consumption of more than 20 g per day for females and 30 g per day for males)
16. Drug abuse or positive drug screening
17. Blood donation of more than 100 mL within 30 days of planned administration of trial medication or intended blood donation during the trial
18. Intention to perform excessive physical activities within one week prior to the administration of trial medication or during the trial
19. Inability to comply with the dietary regimen of the trial site
20. A marked baseline prolongation of QT/QTc interval (such as QTc intervals that are repeatedly greater than 450 ms in males or repeatedly greater than 470 ms in females) or any other relevant ECG finding at screening
21. A history of additional risk factors for *Torsade de Pointes* (such as heart failure, hypokalaemia, or family history of Long QT Syndrome)
22. Subject is assessed as unsuitable for inclusion by the investigator, for instance, because the subject is not considered able to understand and comply with study requirements, or has a condition that would not allow safe participation in the study

Female subjects will not be allowed to participate, if any of the following apply:

23. Positive pregnancy test, pregnancy, or plans to become pregnant within 30 days after study completion
24. Lactation

In addition, the following trial-specific exclusion criteria apply:

25. History of asthma or obstructive pulmonary disease
26. Clinically relevant cardiac conduction disorders such as sinoatrial or higher degree atrioventricular block and sick sinus syndrome.
27. Bladder outflow obstruction
28. Subjects with increased risk for developing gastrointestinal ulcers (e.g. those with a history of ulcer disease or frequent use of non-steroidal anti-inflammatory drugs)
29. History of macular degeneration or any abnormal finding in visual tests (Amsler grid test, colour discrimination test) at screening
30. Subjects with known hypersensitivity to piperidine derivatives (e.g. astemizol, loratadin, pethidin, loperamid, haloperidol, domperidon)
31. Liver tests (ALT, AST, GGT, AP), Total Bilirubin or Creatinine outside the normal range at the screening examination

Specifically for Part 2:

32. Any suicidal ideation of type 2 to 5 on the C-SSRS in the past 12 months (i.e. active suicidal thought, active suicidal thought with method, active suicidal thought with intent but without specific plan, or active suicidal thought with plan and intent)
33. Any lifetime history of suicidal behaviour (i.e. actual attempt, interrupted attempt, aborted attempt, or preparatory acts or behaviour).

For study restrictions, refer to [Section 4.2.2](#).

3.3.4 Withdrawal of subjects from treatment or assessments

Subjects may discontinue trial treatment or withdraw consent to trial participation as a whole ('withdrawal of consent') with very different implications; please see [Sections 3.3.4.1](#) and [3.3.4.2](#) below.

If a subject is removed from or withdraws from the trial prior to the first administration of trial medication, the data of this subject will not be entered in the case report form (CRF) and will not be reported in the clinical trial report (CTR). If a subject is removed from or withdraws from the trial after the first administration of trial medication, this will be documented and the reason for discontinuation must be recorded in the CRF; in addition, the data will be included in the CRF and will be reported in the CTR. At the time of discontinuation, a complete end of trial examination will be performed, if possible, and the information will be recorded in the CRF. If the discontinuation occurs before the end of the REP (see [Section 1.2.3](#)), the discontinued subject should if possible be questioned for AEs and concomitant therapies at or after the end of the REP in order to ensure collection of AEs

and concomitant therapies throughout the REP, if not contrary to any consent withdrawal of the subject.

If it is known that a subject becomes pregnant during the trial, administration of the trial medication is to be stopped immediately, and the subject is to be removed from the trial. The subject is to be followed until she has given birth or until the end of the pregnancy. The subject's data are to be collected until the end of the trial (last visit of last subject) and reported in the CTR. For reporting of pregnancy and associated events, refer to [Section 5.2.7.2.4](#).

3.3.4.1 Discontinuation of trial treatment

An individual subject will discontinue trial treatment if:

- The subject wants to discontinue trial treatment, without the need to justify the decision
- The subject has repeatedly shown to be non-compliant with important trial procedures and, in the opinion of both, the investigator and sponsor representative, is not willing or able to adhere to the trial requirements in the future.
- The subject needs to take concomitant medication that interferes with the investigational medicinal product or other trial treatment
- The subject can no longer receive trial treatment for medical reasons (such as pregnancy, surgery, adverse events [AEs], or diseases)
- The subject has an elevation of AST and/or ALT ≥ 3 -fold ULN OR an elevation of total bilirubin ≥ 2 -fold ULN (measured in the same blood sample) and/or needs to be followed up according to the DILI checklist provided in the ISF
- The subject shows signs and symptoms of cholinergic crisis or neuroleptic malignant syndrome (see [Section 1.2.2](#)).
- The subject exhibits serious suicidality, in the clinical judgment of the investigator or according to the following criteria:
 - any suicidal behaviour (i.e. actual attempt, interrupted attempt, aborted attempt, or preparatory acts or behaviour)
 - any suicidal ideation of type 4 or 5 in the C-SSRS (i.e. active suicidal thought with intent but without specific plan, or active suicidal thought with plan and intent)

In addition to these criteria, the investigator may discontinue subjects at any time based on his or her clinical judgment.

Even if the trial treatment is discontinued, the subject remains in the trial and, given his/her agreement, will undergo the procedures for early treatment discontinuation and follow up as outlined in the [Flow Chart](#) and [Section 6.2.3](#).

3.3.4.2 Withdrawal of consent to trial participation

Subjects may withdraw their consent to trial participation at any time without the need to justify the decision. If a subject wants to withdraw consent, the investigator should be involved in the discussion with the subject and explain the difference between trial treatment discontinuation and withdrawal of consent to trial participation, as well as explain the options for continued follow up after trial treatment discontinuation, please see [Section 3.3.4.1](#) above

3.3.4.3 Discontinuation of the trial by the sponsor

Boehringer Ingelheim reserves the right to discontinue the trial at any time for any of the following reasons:

- Failure to meet expected enrolment goals overall or at a particular trial site
- New toxicological findings, serious adverse events, or any safety information invalidating the earlier positive benefit-risk-assessment. More specifically, the trial will be terminated if more than 50% of the subjects have drug-related and clinically relevant adverse events of moderate or severe intensity, or if at least 1 drug-related serious adverse event is reported
- Violation of GCP, or the CTP, or the contract with BI impairing the appropriate conduct of the trial
- The sponsor decides to discontinue the further development of the investigational product
- The investigator / trial site will be reimbursed for reasonable expenses incurred in case of trial termination (except if item 3 applies).

3.3.5 Replacement of subjects

In case more than 2 subjects per Part discontinue treatment, the Clinical Trial Leader together with the Trial Pharmacokineticist and the Trial Statistician are to decide, if and how many subjects will be replaced. A replacement subject will be assigned a unique trial subject number, and will be assigned to the same treatment as the subject he or she replaces.

4. TREATMENTS

4.1 INVESTIGATIONAL TREATMENTS

The investigational products have been manufactured by BI Pharma GmbH & Co. KG (BI 425809) and by Ratiopharm GmbH, Germany (donepezil).

4.1.1 Identity of the Investigational Medicinal Products

The characteristics of the trial products are given below:

Trial product 1:

Substance:	BI 425809
Pharmaceutical formulation:	Film coated tablet
Source:	BI Pharma GmbH & Co. KG, Germany
Unit strength:	25 mg
Posology:	Part 1: 0-0-1 Part 2: 1-0-0
Route of administration:	Oral
Duration of use:	Part 1: single dose on Day 1, Visit 2, and on Day 22, Visit 3 Part 2: multiple doses on days 1-24, Visit 3

Trial product 2:

Name:	Donepezil-HCl-ratiopharm®
Substance:	Donepezil
Pharmaceutical formulation:	Film-coated tablet
Source:	Ratiopharm GmbH, Germany
Unit strength:	5 mg
Posology:	Part 1: 0-0-1 (Days 1-7, Visit 3) and 0-0-2 (Days 8-28, Visit 3) Part 2: 2-0-0
Route of administration:	Oral
Duration of use:	Part 1: multiple doses on days 1-28, Visit 3 Part 2: single dose on Day 1, Visit 2 and on Day 10, Visit 3

4.1.2 Selection of doses in the trial

The donepezil dose selected for this trial is the standard clinical dose [[R18-3913](#)] and the chosen up-titration scheme is recommended to improve tolerability. The dose selected for

BI 425809 is the highest dose to be tested in the ongoing Phase 2 and presumably in the following Phase 3 trials.

4.1.3 Method of assigning subjects to treatment groups

Both parts of the trial are designed as open-label, fixed sequence. All subjects participating in one Part will receive the same treatment sequence.

Reference and test treatments will be administered in the sequence specified in the [Flow Chart](#).

Once a subject number has been assigned, it cannot be reassigned to any other subject.

All subjects may be treated in one cohort, i.e. all subjects may receive treatment on the same calendar day. In case this is not feasible (e.g., due to logistical or recruitment reasons), the group may be split into several cohorts as required.

The following procedure regarding reserve subjects applies:

Reserve subjects will attend the Screening Visit and follow all trial procedures up to treatment allocation on Day 1, but will not be dosed unless they replace a subject who does not fulfill the requirements of the trial before administration of the IMP, i.e. they will remain at the trial site until all intended subjects have been allocated to treatment. They will be informed that they will be reserve subjects.

4.1.4 Drug assignment and administration of doses for each subject

This trial consists of two parts:

Part 1 is an open-label, two-treatment, two-period, one fixed sequence cross-over trial, in which all subjects will first receive BI 425809 (treatment A = Reference 1) alone and then again after multiple doses of donepezil (treatment B = Test 1).

The treatments to be evaluated in Part 1 are outlined in [Table 4.1.4: 1](#) below.

Table 4.1.4: 1 Part 1: Dosage and treatment schedule

Treatment	Substance	Formulation	Unit strength	Dosage	Total dose
A (Reference 1)	BI 425809	Tablet	25 mg	1 tablet (Day 1, Visit 2)	25 mg
B (Test 1)	Donepezil	Tablet	5 mg	1 tablet (Day 1-7, Visit 3) q.d. 2 tablets (Day 8-28, Visit 3) q.d.	245 mg
	BI 425809	Tablet	25 mg	1 tablet (Day 22, Visit 3)	25 mg

Part 2 has an open-label two-treatment, two-period, one fixed-sequence cross-over design. In Part 2 all subjects will first receive donepezil (treatment C = Reference 2) alone and then again after multiple doses of BI 425809 (treatment D = Test 2).

The treatments to be evaluated in Part 2 are outlined in [Table 4.1.4: 2](#) below.

Table 4.1.4: 2 Part 2: Dosage and treatment schedule

Treatment	Substance	Formulation	Unit strength	Dosage	Total dose
C (Reference 2)	Donepezil	Tablet	5 mg	2 tablets (Day 1, Visit 2)	10 mg
D (Test 2)	Donepezil	Tablet	5 mg	2 tablets (Day 10, Visit 3)	10 mg
	BI 425809	Tablet	25 mg	1 tablet (Days 1-24, Visit 3) q.d.	600 mg

Trial medication will be administered to fasted subjects only (for fasting periods please refer to [Section 4.2.2.2](#)). The investigator (or authorised designee) will administer the trial medication as an oral dose together with about 240 mL of water to subjects who are in a standing position. For drug administration, the so-called four-eye principle (two-person rule) should be applied. For this, one authorised employee of the trial site should witness the administration of trial medication, and – if applicable – its preparation (e.g. reconstitution), if correct dosage cannot be ensured otherwise.

In **Part 1**, subjects will be kept under close medical surveillance until 38 h following administration of BI 425809 on Day 1, Visit 2 and on Day 22 Visit 3. In addition subjects will remain under medical supervision for about 14 h following the first dose of donepezil on Day 1 Visit 3. This in-house surveillance period can be extended anytime if deemed necessary based on the medical judgement of the investigator.

In **Part 2**, subjects will be kept under close medical surveillance until at least 72 h following administration of donepezil on Day 1(Visit 2) and Day 10 (Visit 3).

There will be no wash-out period between treatments A/C and B/D in Part 1 and 2, respectively as the extended blood sampling phase already covers a sufficiently long wash-out between the drug administration of treatment A/C and the first drug administration in treatment B/D. Therefore the first day of treatment B/D, i.e. Visit 3, follows immediately after the last day of treatment A/C, i.e. Visit 2, but these two days are not the same day.

For restrictions with regard to diet see [Section 4.2.2.2](#).

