Trial endpoints:	Primary endpoints: 
 • Part 1: AUC_{0-∞} and C_{max} of BI 425809 • Part 2: AUC_{0-∞} and C_{max} donepezil Secondary endpoints: 
 • Part 1: AUC_{0-tz} of BI 425809 • Part 2: AUC_{0-tz} of donepezil
Number of subjects	
total entered	N = 32
each treatment	Part 1: N = 18 Part 2: N = 14
Diagnosis	Not applicable
Main criteria for inclusion	Healthy male/female subjects, age of 18 to 50 years (inclusive), body mass index (BMI) of 18.5 to 29.9 kg/m ² (inclusive)

FLOW CHART

Part 1

Visit*	Day	Planned time (relative to first drug administration [h:min])	Approximate clock time of actual day [h:min]	Event and comment	Safety laboratory	PK _{plasma} (BI 425809)	PK _{plasma} Donepezil	Safety assessments	12-lead ECG ¹⁴	Vital signs (BP, PR) ¹⁴	Questioning for AEs and concomitant therapy ⁶		
1	-21 to -1	n.a.	n.a.	Screening ¹	x ¹⁰			x ^{12,13}	x	x			
	-3 to -1	-24:00	n.a.		x ⁹						x		
	2 (Treatment A)	1	-10:00	08:00	Admission to trial site	x ¹⁵				x	x	x ⁷	
			00:00	18:00	Drug administration, 25 mg BI 425809		x ²						
			00:30	18:30			x						
			01:00	19:00			x						
			02:00	20:00	240ml fluid intake		x						
			03:00	21:00			x						
			03:30	21:30			x						
		04:00	22:00	240 mL fluid intake, Dinner, thereafter start of bed rest ¹⁶		x				x	x	x	
		04:30	22:30			x							
		05:00	23:00			x							
		2	06:00	00:00			x						
			08:00	02:00			x						
			10:00	04:00			x						
	12:00		06:00	End of bed rest ¹⁶ , Breakfast ³		x				x	x	x	
	3	24:00	18:00			x						x	
		34:00	04:00			x						x	
	3	38:00	08:00	Discharge ¹¹					x	x	x	x	
		48:00	18:00	Ambulatory visit		x						x	
4	72:00	18:00	Ambulatory visit		x						x		
5	96:00	18:00	Ambulatory visit	x ¹⁰	x						x		
6	120:00	18:00	Ambulatory visit		x						x		
7	144:00	18:00	Ambulatory visit		x						x		
8	168:00	18:00	Ambulatory visit	x ¹⁰	x						x		
3 (Treatment B)	1	-02:00	16:00	Admission to trial site	x ¹⁵						x		
		00:00	18:00	Admin. 5 mg donepezil			x ²		x ²	x ²	x ^{2,7}		
	2	14:00	08:00	Discharge ¹¹					x	x	x		
		24:00	18:00	Ambulatory visit ¹¹ , admin. 5 mg donepezil					x ²	x ²	x ^{2,7}		
	3	48:00	18:00	Ambulatory visit ¹¹ , admin. 5 mg donepezil							x ^{2,7}		
	4	72:00	18:00	Ambulatory visit ¹¹ , admin. 5 mg donepezil	x ¹⁰				x ²	x ²	x ^{2,7}		
	5	96:00	18:00	Ambulatory visit ¹¹ , admin. 5 mg donepezil							x ^{2,7}		
	6	120:00	18:00	Ambulatory visit ¹¹ , admin. 5 mg donepezil					x ²	x ²	x ^{2,7}		

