	7	144:00	18:00	Ambulatory visit ¹¹ , admin. 5 mg donepezil			x ⁸				x ^{2,7}		
	8	168:00	18:00	Ambulatory visit ¹¹ , admin. 10 mg donepezil	x ¹⁰			x ¹²	x ²	x ²	x ^{2,7}		
	9	192:00	18:00	Ambulatory visit ¹¹ , admin. 10 mg donepezil							x ^{2,7}		
	10	216:00	18:00	Ambulatory visit ¹¹ , admin. 10 mg donepezil							x ^{2,7}		
	11	240:00	18:00	Ambulatory visit ¹¹ , admin. 10 mg donepezil							x ^{2,7}		
	12	264:00	18:00	Ambulatory visit ¹¹ , admin. 10 mg donepezil	x ¹⁰				x ²	x ²	x ^{2,7}		
13	288:00	18:00	Ambulatory visit ¹¹ , admin. 10 mg donepezil							x ^{2,7}			
14	312:00	18:00	Ambulatory visit ¹¹ , admin. 10 mg donepezil			x ⁸				x ^{2,7}			

Visit	Day	Planned time (relative to first drug administration [h:min])	Approximate clock time of actual day [h:min]	Event and comment	Safety laboratory	PK _{plasma} (BI 425809)	PK _{plasma} Donepezil	Safety assessments	12-lead ECG ¹⁴	Vital signs (BP, PR) ¹⁴	Questioning for AEs and concomitant therapy ⁶	
3 (Treatment B)	15	336:00	18:00	Ambulatory visit ¹¹ , admin. 10 mg donepezil							x ^{2,7}	
	16	360:00	18:00	Ambulatory visit ¹¹ , admin. 10 mg donepezil	x ¹⁰			x ¹²	x ²	x ²	x ^{2,7}	
	17	384:00	18:00	Ambulatory visit ¹¹ , admin. 10 mg donepezil							x ^{2,7}	
	18	408:00	18:00	Ambulatory visit ¹¹ , admin. 10 mg donepezil							x ^{2,7}	
	19	432:00	18:00	Ambulatory visit ¹¹ , admin. 10 mg donepezil	x ¹⁰		x ⁸		x ²	x ²	x ^{2,7}	
	20	456:00	18:00	Ambulatory visit ¹¹ , admin. 10 mg donepezil			x ⁸				x ^{2,7}	
	21	480:00	18:00	Ambulatory visit ¹¹ , admin. 10 mg donepezil			x ⁸				x ^{2,7}	
	22	494:00	08:00	Admission to trial site	x ^{5,10}				x ¹²	x	x	x ^{2,7}
		504:00	18:00	Drug administration, 25 mg BI 425809 + 10 mg donepezil		x ⁸	x ⁸					x ^{2,7}
		504:30	18:30			x						
		505:00	19:00			x						
		506:00	20:00	240 ml fluid intake		x						
		507:00	21:00			x						
		507:30	21:30			x						
		508:00	22:00	240 mL fluid intake, Dinner, thereafter start of bed rest ¹⁶		x				x	x	x
		508:30	22:30			x						
		509:00	23:00			x						
	23	510:00	00:00			x						
		512:00	02:00			x						
		514:00	04:00			x						
		516:00	06:00	End of bed rest ¹⁶ , Breakfast ³		x				x	x	x
		528:00	18:00	Drug administration, 10 mg donepezil		x				x ²	x ²	x ^{2,7}
	24	540:00	06:00			x						x ^{2,7}
		542:00	08:00	Discharge ¹¹					x ¹²	x	x	x ⁷
		552:00	18:00	Ambulatory visit ¹¹ , admin. 10 mg donepezil		x ⁸						x ^{2,7}
	25	576:00	18:00	Ambulatory visit ¹¹ , admin. 10 mg donepezil	x ¹⁰	x ⁸	x ⁸		x ²	x ²	x ^{2,7}	

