	26	600:00	18:00	Ambulatory visit ¹¹ , admin. 10 mg donepezil		x ⁸					x ^{2,7}	
	27	624:00	18:00	Ambulatory visit ¹¹ , admin. 10 mg donepezil		x ⁸					x ^{2,7}	
	28	648:00	18:00	Ambulatory visit ¹¹ , admin. 10 mg donepezil		x ⁸					x ^{2,7}	
29	672:00	18:00	Ambulatory visit ¹¹	x ¹⁰	x ⁸			x ²	x ²	x ^{2,7}		
4	44-49	n.a.	n.a.	End of trial examination ⁴	x ¹⁰			x ^{12,13}	x	x	x	

1. Screening includes subject information, informed consent, physical examination including neurological assessment, check of vital signs, visual tests, ECG, safety laboratory (including drug screening, alcohol breath test, urine pregnancy testing in females, and faecal occult blood test), demographics (including determination of body height and weight, smoking status and alcohol history), relevant medical history, concomitant therapy and review of inclusion/exclusion criteria.
2. The time is approximate; the procedure is to be performed and completed within 2 h prior to drug administration.
3. If several actions are indicated at the same time point, the intake of meals will be the last action.
4. End of trial examination includes physical examination including neurological assessment, vital signs, visual tests, ECG, safety laboratory, urine pregnancy testing in females, recording of AEs and concomitant therapies, faecal occult blood test.
5. Including urine drug screening and alcohol breath test and urine pregnancy testing in females
6. AEs and concomitant therapies will be recorded throughout the trial, but will be specifically asked for at the time points indicated in the [Flow Chart](#) above.
7. Includes questioning for 'restrictions'

8. Pre-dose PK, i.e. within 10 min prior to the next drug administration
9. Safety laboratory to be taken within 3 days prior to first trial drug administration of Visit 2 and 3. All results must be available and be checked by the investigator or his/her designee before trial drug administration. For Visit 3, the safety laboratory of day 8, Visit 2 will be used.
10. Includes immunochemical faecal occult blood (iFOB) test
11. Discharge after confirmation of fitness by the investigator/designee
12. Neurological assessment (i.e. Romberg and Unterberger test, assessment of gait, further tests as needed) to be performed at the time points mentioned in the [Flow Chart](#) above and at any times CNS adverse events are reported

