1.2.2 Donepezil

Donepezil is a specific and reversible inhibitor of acetylcholinesterase, the predominant cholinesterase in the brain. Current theories on the pathogenesis of the cognitive signs and symptoms of Alzheimer's disease attribute some of them to a deficiency of cholinergic neurotransmission [R15-4794]. Donepezil is indicated for the symptomatic treatment of mild to moderate dementia of the Alzheimer's type and commonly used in this patient population [R18-3913].

In mild to moderate AD the dosing recommendation is a daily dose of 5 mg q.d. which might be increased to a maximum dose of 10 mg q.d.. For tolerability reasons, it is recommended to administer donepezil in the evening and to use an up-titration scheme starting with 5 mg donepezil q.d. and increasing to 10 mg q.d. if needed and well tolerated.

Maximum plasma levels after administration of 10 mg donepezil are reached approximately 3 - 4 hours after oral administration [R15-4794, R18-3913].

The terminal disposition half-life is approximately 70 hours. Following multiple dose administration, steady state is reached within ~3 weeks. Donepezil is mainly excreted (57%) in the urine, both intact (17%) and metabolized, and also via faeces (14.5%). It is extensively metabolized to four major metabolites, of which one, 6-O-Desmethyl-Donepezil has a comparable activity to donepezil, and a number of minor metabolites, of which not all have been identified [R18-3913].

In vitro studies have shown that CYP3A4 and to a minor extent CYP2D6 are involved in the metabolism of donepezil. In a study in healthy volunteers, ketoconazole increased mean donepezil concentrations by about 30 %. In patients with mild – moderate hepatic impairment steady state exposures of donepezil were increased (AUC up to ~ 48%, C_{max} up to ~39%) [R18-3913].

Enzyme inducers such as rifampicin, phenytoin, carbamazepine and alcohol may reduce the levels of donepezil [R15-4794].

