Regarding donepezil, no inhibition of the metabolism of drugs metabolized by CYP-450 isoenzymes is expected at therapeutic doses of donepezil ([Section 1.2.2](#)).

In summary, a clinically relevant pharmacokinetic interaction causing elevated exposures of donepezil or BI 425809 is considered unlikely.

Safety measures

- Close monitoring of
 - Adverse events
 - Safety lab (special focus on hepatic parameters, markers of GI bleeding (CRP, haematology, iFOB), CK)
 - ECG (focus on possible vagotonic action of donepezil)
 - Vital signs
- Prohibition to use drugs as concomitant therapy that are known to also trigger gastrointestinal ulcers/hemorrhage, e.g. NSAIDs ([Section 4.2.2](#))
- Availability of rescue medication (atropine) in case of signs and symptoms of cholinergic crisis (see [Section 4.2.1](#)).
- Subjects will receive a trial specific emergency card with information for anesthesiologists about the donepezil intake in case of unplanned surgery and potential use of succinylcholine
- As donepezil may impact the ability to operate vehicles and/or machines, subjects participating in Part 1 of this trial subjects are not allowed to drive a vehicle or operate machines during Visit 3
- Although only healthy subjects are allowed to enter this trial per se the investigator has to specifically ask subject's for any life-time history of asthma or seizure resulting in exclusion of the subject

Although rare, a potential for drug-induced liver injury is under constant surveillance by sponsors and regulators. Therefore, this study requires timely detection, evaluation, and follow-up of alterations in selected liver laboratory parameters to ensure subjects' safety.

Overall assessment

Considering the good safety profile of BI 425809 observed so far in healthy subjects, and the safety and tolerability of donepezil up to single doses of 23 mg in healthy volunteers, the unlikelihood of increased drug exposures due to a donepezil-BI 425809 interaction and taking into account the safety measures described in this chapter, the benefit of a successful clinical development of BI 425809 for the treatment of Alzheimer's disease or CIAS is assessed to outweigh the potential risks to healthy subjects participating in this trial that are further considered to be low and acceptable.

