7.3.4 Safety analyses

Safety will be analysed based on the assessments described in [Section 2.2.2.2](#). All treated subjects (TS, refer to [Section 7.2](#)) will be included in the safety analysis. Safety analyses will be descriptive in nature and based on BI standards. No hypothesis testing is planned.

For all analyses, the treatment actually administered (= treatment at onset) to the subject will be used (any deviations from the randomised treatment will be discussed in the minutes of the Report Planning Meeting).

Treatments will be compared in a descriptive way. Tabulations of frequencies/proportions will be used to evaluate categorical (qualitative) data, and tabulations of descriptive statistics will be used to analyse continuous (quantitative) data.

Measurements (such as vital signs, or laboratory parameters) or AEs will be assigned to treatments (see [Section 4.1](#)) based on the actual treatment at the planned time of the measurement or on the recorded time of AE onset (concept of treatment emergent AEs). Therefore, measurements planned or AEs recorded prior to first intake of trial medication will be assigned to the screening period, those between first trial medication intake and end of REP (see [Section 1.2.3](#)) will be assigned to the treatment period. Events occurring after the REP but prior to next intake or end of trial termination date will be assigned to 'follow-up'. In case of two or more treatments, the follow-up will be summarized according to the previous treatment. These assignments including the corresponding time intervals will be defined in detail in the TSAP. Note that AEs occurring after the last per protocol contact but entered before final database lock will be reported to Pharmacovigilance only and will not be captured in the trial database.

Additionally, further treatment intervals (analysing treatments) may be defined in the TSAP in order to provide summary statistics for time intervals, such as combined treatments, on-treatment totals, or periods without treatment effects (such as screening and follow-up intervals).

Adverse events will be coded using the Medical Dictionary for Regulatory Activities (MedDRA). Frequency, severity, and causal relationship of AEs will be tabulated by treatment, system organ class, and preferred term. SAEs, AESIs (see [Section 5.2.7.1](#)), and other significant AEs (according to ICH E3) will be listed separately.

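### Part 1 keeps subjects in-house for about 14 h after the first donepezil dose but schedules no ECG, vital signs or AE questioning before discharge

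*Protocol*

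**What the plan says.** **The stay.** Protocol Section 4.1.4: "In addition subjects will remain under medical supervision for about 14 h following the first dose of donepezil on Day 1 Visit 3". In the Flow Chart for Part 1, Visit 3 Day 1, the dosing row ("Admin. 5 mg donepezil") is at 00:00, clock time 18:00. Its ECG, vital-sign and AE-questioning marks carry footnote 2: "The time is approximate; the procedure is to be performed and completed within 2 h prior to drug administration". The next row is discharge at 14:00 (08:00 on Day 2), with ECG, vital signs and AE questioning.

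**The peak.** Section 1.2.2: "Maximum plasma levels after administration of 10 mg donepezil are reached approximately 3 - 4 hours after oral administration".

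**The monitoring promise.** Section 1.4 lists, under close monitoring, "ECG (focus on possible vagotonic action of donepezil". Section 1.2.2 names bradycardia, sino-atrial and atrioventricular block and syncope among donepezil's effects.

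**The analysis.** Section 7.3.4 of the protocol: "Treatments will be compared in a descriptive way". The SAP summarises vital signs descriptively by planned time point (7.8.3) and reports ECG findings only as AEs or baseline conditions (7.8.4). SAP Table 6.1: 3 defines the Part 1 analysis phases.

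**The concern.** The overnight stay surrounds the expected peak of the first donepezil dose, yet nothing is scheduled near it. A short-lived, symptomless fall in pulse or a conduction change at 3 to 4 h would be recorded only if someone chose to look. The Flow Chart does place an ECG and vital signs at 4 h after every PK-profile dose in both parts, and no reason is given for leaving them out here. At stake is first-dose safety observation in the 18 Part 1 subjects. In addition, a reader of the CTR should know how late after dosing all the Part 1 donepezil-alone readings were taken.

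**Working it through.** **Step 1: the plan's own figure.** 18:00 on Day 1 to 08:00 on Day 2 is 14 h, which agrees with Section 4.1.4.

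**Step 2: dose times.** Visit 3 has 28 daily donepezil doses, dose *j* at 24(*j* − 1) h. The total is 7 × 5 + 21 × 10 = 245 mg, which agrees with Table 4.1.4: 1. Day 22 (504:00) is the combined dose; the other 27 are donepezil only.

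**Step 3: time from the preceding dose to each ECG and vital-sign reading (Flow Chart, Part 1 Visit 3).**

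| Reading | Preceding dose | Hours after it |
|---|---|---|
| 14:00 | Day 1, 00:00 | 14 |
| 24:00, 72:00, 120:00, 168:00, 264:00, 360:00, 432:00 | day before | 22 to 24 (footnote 2) |
| 494:00 | Day 21, 480:00 | 14 |
| 508:00 | Day 22, 504:00 (combined) | 4 |
| 516:00 | Day 22, 504:00 (combined) | 12 |
| 542:00 | Day 23, 528:00 | 14 |

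Before the combined dose, 0 of 9 readings are earlier than 14 h after a dose; two fall at 14 h exactly. Section 6.1 allows ±1 h, so the earliest could be at 13 h. The doses after Day 22 add nothing earlier: 542:00 is at 14 h, and 576:00 and 672:00 are at 22 to 24 h.

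**Step 4: the 4 h reading elsewhere.** ECG and vital signs are marked at 04:00 in Part 1 Visit 2, at 508:00 in Part 1 Visit 3 (508 − 504 = 4), at 04:00 in Part 2 Visit 2, and at 220:00 in Part 2 Visit 3 (220 − 216 = 4). That is four of four profile doses.

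**Step 5: could a 4 h reading on Visit 3 Day 1 also serve as the donepezil-alone comparator for 508:00?**

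- *Phase.* Visit 3 Day 1 is the day after Visit 2 Day 8, so the first donepezil dose is 168 + 24 = 192 h after BI 425809. The reading would be at 192 + 4 = 196 h, inside the residual effect period of 11 × 24 = 264 h. SAP Table 6.1: 3 therefore assigns it to Don + BI part 1.
- *Exposure.* Assume mono-exponential decline from 4 h with the stated half-life of about 70 h, and set the 4 h level per mg to 1. Then f(t) = 2^(−(t − 4)/70), so f(14) = 0.91 and f(24) = 0.82. Over one day r = 2^(−24/70) = 0.788. Summing the doses:
  - 508:00: 10(1 − r^15)/(1 − r) + 5r^15(1 − r^7)/(1 − r) = 46.5
  - 494:00: f(14) × [10(1 − r^14)/(1 − r) + 5r^14(1 − r^7)/(1 − r)] = 41.9
  - 4 h after the first 5 mg dose: 5.0
- *Ratios.* 5.0/46.5 = 11%; 41.9/46.5 = 90%.

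The answer is no. The existing 494:00 reading is far closer in exposure to 508:00 than the added one would be.

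**The case against.** The case for leaving the schedule alone is fair in several respects. Visit 3 Day 1 is not a PK-profile day. Subjects are under medical supervision that night and the stay can be extended (Section 4.1.4). AEs are recorded throughout (Flow Chart footnote 6), and unscheduled ECGs are permitted (Section 5.2.6). Section 1.4 names no post-dose time, and the peak time is stated for 10 mg. Part 2 Treatment C does measure ECG and vital signs at 4 h and 12 h after 10 mg donepezil alone. All of this stands, and it keeps the point small: no stated requirement is breached. It does not close the gap. Supervision and spontaneous reports do not reliably catch a symptomless change, and the Part 2 readings come from other subjects after a single morning dose.

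A reader might infer more: that the 4 h reading after the combination has no donepezil-alone counterpart in Part 1, so a donepezil effect could be mistaken for a combination effect, and that the extra row would cure this. The documents do not support that. On the assumption in Step 5, a donepezil-alone reading at about 90% of the 508:00 level already exists. The extra reading would be at about 11% and would carry the combination label. The safety objective concerns BI 425809 (Section 2.2.2.2), for which the 4 h and 12 h readings match between BI 425809 alone and the combination. The comparison is descriptive, with no hypothesis test.

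**Conclusion.** The point holds as a first-dose safety matter only. The Flow Chart schedules no ECG, vital signs or AE questioning between the pre-dose row and discharge at 14 h on Visit 3 Day 1, for all 18 Part 1 subjects. That does not fit Section 1.4, the stated peak time, or the trial's own 4 h practice. It is a cheap improvement rather than an error: the PK endpoints and their analysis are unaffected.

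The finding rests on reading footnote 2 as pre-dose and on taking the 10 mg peak time as a guide for 5 mg, for which the documents give none. The exposure ratios, used only to reject the comparator argument, ignore absorption and distribution. A distribution phase would widen the gap between peak and later levels, and the documents do not quantify one.

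**What to change.** Reconcile the Flow Chart with Section 1.4 by adding a 04:00 row (22:00 clock time) to Part 1 Visit 3 Day 1 with ECG, vital signs and AE questioning. Report it by planned time point under its SAP phase, Don + BI part 1, and do not present it as a donepezil-alone value.

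In the CTR, state that the Part 1 donepezil-alone vital signs all come from 14 h or later after a dose, that 494:00 is the closest in exposure to the 4 h reading after the combination, and that Part 2 Treatment C supplies readings at 4 h and 12 h after 10 mg donepezil alone.

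The cost is one ECG, one vital-sign set and one round of AE questioning in each of 18 subjects already on site. There is no extra visit, equipment or blood; the downside is one more evening measurement. If the Part 1 first doses have already been given, only the CTR note remains, at no cost to subjects.
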